**ABSTRACT**

Some smokers who try e-cigarettes transition completely from cigarettes to e-cigarettes, but others continue to use both products, or abandon e-cigarettes and return completely to cigarettes. One factor that likely impacts these tobacco use patterns is the e-cigarette device used. The majority of e-cigarettes purchased today are one of two “types:” customizable tanks or pods. These e-cigarette types differ from each other in critical ways, like nicotine delivery and sensory characteristics, that are likely to impact use by influencing the relative reinforcement value of the product. The present study will be a randomized trial investigating the impact of e-cigarette device type on reinforcement value and use among current smokers. Current smokers (n=100) will be randomly assigned to either a control group that does not receive an e-cigarette or one of two e-cigarette types: a customizable tank, or a pod. The impact of device type on relative reinforcement value will be assessed using a choice task. Participants will also take home their assigned e-cigarette for a three-week sampling period. Primary outcomes include relative reinforcement value (choices to smoke in the lab-based choice task), cigarette smoking behavior (cigarettes smoked per day during sampling), and uptake (e-cigarette puffing episodes per day during sampling).

## Comparison of leading e-cigarette product types on relative reinforcement value and tobacco use patterns among current smokers

### Specific Aims

The prevalence of e-cigarettes has risen dramatically in the United States, and the impact of these products on public health remains controversial. Proponents of e-cigarettes argue that because e-cigarettes deliver lower levels of toxicants than conventional cigarettes, they may offer reduced health risks for current smokers who switch completely. However, while e-cigarettes appear to offer a path away from smoking for a subset of smokers, a large proportion of those who try e-cigarettes abandon them after a short trial period, or continue to use both products (i.e., dual use). Complete switching from cigarettes to e-cigarettes among those who try them is modest at best. Since the ultimate impact of e-cigarettes is likely dependent on their ability to curb cigarette smoking, it is important to understand the device characteristics (in addition to user characteristics: not studied here) that contribute to their uptake. One major and perhaps most visible device factor that determines uptake is the type of e-cigarette itself. The sheer volume of e-cigarette brands makes it impossible to test the impact of each brand (over 400 estimated brands). However, most e-cigarettes can be categorized into one of four broad types with distinct characteristics: cig-a-likes, tanks, customizable tanks, and pods.

There is strong evidence that cig-a-likes deliver less nicotine, are less satisfying, and are less likely to promote switching than other device types. Thus, these devices are not included in the proposed project. Tank devices have a nicotine delivery profile differs markedly from traditional cigarettes, and thus have also not been included here. The other two types, customizable tanks and pods, corner significant portions of the e-cigarette market and differ from each other in critical ways that would be expected to impact uptake, and thus constitute our primary focus. Customizable tanks deliver nicotine in a profile that more closely models the nicotine delivery of traditional cigarettes. These devices offer a high level of customization that allows users to adjust the device until they reach their desired sensory and nicotine delivery settings. However, the customization renders them relatively complicated to learn to use. Pods (e.g., JUUL) are the newest type of e-cigarette on the market. Pods utilize nicotine salts, rather than free-base nicotine, which the company claims allows them to deliver high levels of nicotine in a profile that is comparable to traditional cigarettes. They offer no customization, making them easy to use. The combination of high nicotine delivery with increased usability may increase the relative reinforcement value of these products, resulting in greater uptake than other device types. **There is almost no existing research that directly compares these device types against each other. The goal of this application is to provide a preliminary assessment comparing e-cigarette device types (customizable tanks, pods) in a head-to-head design.**

In a between-subjects design, adult daily smokers (n=100) who are interested in trying e-cigarettes will be randomly assigned in 1:2:2 fashion to either a control group that receives no product (n=20), or to receive one of two types of e-cigarettes to sample over a three-week period: a) customizable tank, or b) pod, (n=40/group). The design is naturalistic in that participants receiving an e-cigarette will be told to use the e-cigarette as much or as little as they would like, allowing for assessment of self-determined uptake and reinforcement. Methods include both ecological assessments (electronic daily diaries) and experimental sessions (choice and purchase tasks). Biomarkers (expired carbon monoxide) will corroborate self-reported indices of use.

**Primary Specific Aim:** to assess the impact of e-cigarette product type (customizable tanks vs. pods) on product satisfaction ratings and relative reinforcement value (choices to smoke vs. use product in choice task, hypothetical purchase task). We hypothesize that pods will produce greater satisfaction ratings and relative reinforcement value than the customizable tanks.

**Secondary Aim:** to assess the impact of e-cigarette product type on tobacco use patterns including cigarette smoking (cigarettes per day, expired breath carbon monoxide) and e-cigarette uptake (e-cigarette puffing episodes). We hypothesize that pod style e-cigarettes will produce greater reductions in cigarette smoking compared to customizable tanks and greater uptake of e-cigarettes. Secondary analyses will compare the impact of e-cigarette sampling (control vs. all e-cigarette groups) on smoking during the sampling period.

**Relevance to Tobacco Regulation:** We recognize that e-cigarette device types differ from each other in multiple ways, and it will not be possible to isolate the mechanism by which one type performed better than others (e.g., nicotine delivery, appearance, customization). We view device heterogeneity as a strength since this design mimics the real-world options that smokers face when adopting e-cigarettes but with randomized design to enhance rigor. The goal here is to provide useful information to regulatory agencies and consumers about which types provide the highest reinforcement value and lead to the greatest uptake, *inclusive of the differences between types*. Understanding the impact of device type would provide guidance about which e-cigarette smokers might choose, while at the same time providing key information to the FDA about how to better regulate

e-cigarettes for the improvement of public health. This proposal is in line with funding opportunities from FDA and NIDA.

## Significance

**A1. Patterns of E-cigarette Use:** E-cigarettes have dramatically risen in popularity in recent years. Proponents of e-cigarettes argue that because e-cigarettes deliver lower levels of toxicants than conventional cigarettes, they could offer reduced health risks for current smokers who switch completely. However, the impact of e-cigarettes on cigarette smoking remains largely unknown.

**A2. The Impact of Product Type on Reinforcement Value and Use:** Smokers have 400+ different e-cigarette brands from which to choose, which vary across many characteristics including appearance, nicotine concentration, device power, flavoring, e-liquid constituents, potential for customization, throat hit, and volume of aerosol production. Full scientific evaluation of these characteristics would be difficult. Instead, we believe it is better and more ecologically valid to test different *types of products*. Here, we focus on two popular device types that collectively comprise about 90% of the e-cigarette market and can deliver nicotine at levels that are comparable to combustible cigarettes. Customizable tanks use refillable tanks and are activated by pushing a button, but are larger in appearance and offer a high degree of customization to the user (e.g., wattage, resistance, air flow). Pods, the newest category of devices, often resemble a flash drive in appearance, are activated by drawing on the device rather than pushing a button, are low in wattage, and use a high nicotine concentration e-liquid. JUUL, the most popular pod, has recently surged in popularity. These types of devices have different characteristics that are likely to collectively impact the relative reinforcement value of the product in comparison to a current smoker's usual brand. Relative reinforcement value refers to the degree to which users like/enjoy/want/prefer these alternative e-cigarettes, in comparison to combustible cigarettes. Estimates of relative reinforcement (e.g., purchase tasks, preference tasks) are well-established measures of drug abuse liability and have been utilized for making drug-related policy and regulatory decisions. Because the e-cigarette market is changing rapidly, **we know relatively little about the impact of device type on reinforcement value, nor do we have sufficient studies of cross-device comparisons.**

**A2a. Nicotine Formulation, Sensory Characteristics, and Customization Potential:** Pods deliver nicotine using nicotine salts, rather than free-base nicotine used by customizable tanks. There is no published research directly examining the impact of salts on reinforcement or use, but the makers of JUUL, the most popular pod, claim that using nicotine salts allows for high nicotine delivery with a smooth nicotine hit.

Several sensory characteristics may be important. First, because pods devices are low powered devices, they produce less visible aerosol than customizable tanks. Second, the two device types generate different user topographies. Pod devices are often vaped into the mouth before being inhaled into the lung (i.e., mouth-to-lung), while customizable tanks are inhaled directly to the lungs without first lingering in the mouth (i.e., direct-lung). Third, throat hit is often described as an important sensory characteristic of tobacco use, and the two device types may offer throat hits with different strengths.

One of the characteristics that distinguishes customizable tanks from pods is that they are, indeed, highly customizable. No published research has directly examined the impact of e-cigarette customization on reinforcement value or use. We know that in general, people are more motivated to engage in an activity when there is choice involved, but added customization also introduces more complexity, which could lead to decreased uptake. User satisfaction can also be decreased when there are too many options available.

**A3. Scientific Premise:** The ultimate impact of device type on consumer uptake and downstream changes in cigarette use is likely dependent on the combined impact of all of these characteristics (nicotine delivery, sensory characteristics, customization potential), which together function to change the relative reinforcement value of using e-cigarettes compared to smoking. Despite the importance of device type, there are no published studies which directly compare the type of e-cigarette device on reinforcement value or use. Thus, the goal of the proposed IDEA award project is to provide a preliminary assessment, through a randomized design, of the impact of e-cigarette device type on reinforcement value, uptake, and cigarette smoking behavior. We hypothesize that pod e-cigarette devices, which are sleek in appearance, easy to use, have sufficient nicotine delivery, are used in a mouth-to-lung topography that is similar to cigarette smoking, and have a strong throat hit, are likely to generate the highest level of reinforcement value and uptake.

[figure not shown]
Reviewers will be quick to note that any comparison of devices will inherently introduce a number of potential confounds. We view this as a strength, not a weakness. We considered an alternative approach that would hold all aspects of a single device constant and isolate specific e-cigarette characteristics. However, research isolating individual characteristics is also quite limited in its implications because devices differ from each other in multiple ways. The ultimate impact of any given e-cigarette on reinforcement value and use will depend on the *combined effect* of all device and e-liquid characteristics. The proposed research takes a complementary approach which is more ecologically representative of the current market: testing differences in e-cigarette characteristics in the same way consumers experience them, as different device types. Thus, this is the most "real world" cross-product test of different e-cigarettes on behavior.

## A. Innovation

The proposed study is highly innovative, timely, and important given the current landscape. First, this will be the first trial to compare customizable tanks and pods using an experimental design. Large, longitudinal trials, like the Population Assessment of Tobacco and Health, provide information about the relative popularity of these device types. However, these datasets are limited because smokers are not randomized to a specific device, and thus, cannot provide critical information about the causal impact of device type on reinforcement value and use. The randomized design utilized in this study is one of its primary strengths. Second, this project is innovative for its use of the JUUL product specifically. In 2016, JUUL (a popular pod brand) comprised 2% of sales in retail outlets, but that number climbed to 29% in December of 2017 and 76% in November of 2018. Because of how rapid the rise in popularity has been, there is almost no existing research which investigates its impact. To the best of our knowledge, there are no published experimental studies investigating JUUL and no published reports focusing on JUUL use among current smokers.

## C. Approach

**C1. Design and Procedures:** Consented participants will complete screening measures to determine eligibility. Eligible adult smokers will be randomly assigned in a 1:2:2 between-subjects design to either not receive an e-cigarette (control group, n=20) or receive one of two e-cigarette types: a customizable tank, or pods (n=40/each). Participants will sample their assigned e-cigarette, complete questionnaires, and then complete the choice task (described below). Participants will be provided with an e-cigarette device and e-liquid to sample over a three-week period (Figure 1). Across the study, participants will complete daily electronic diaries that assess their daily use of cigarettes and e-cigarettes. Participants will also complete weekly phone calls where they will complete assessments regarding tobacco use, craving, dependence, and product perceptions. At the end of the sampling period, participants will return to the lab to complete a series of questionnaires, complete the sampling and choice tasks again, and return the device.

**C2. Participants:** Daily cigarette smokers (n=100) will be recruited from the community. In/exclusion criteria are designed to enroll smokers who have limited experience with e-cigarettes. Inclusion criteria include adults who a) have been smoking at least five cigarettes daily for the past year (baseline CO > 8ppm), b) rate their interest in using e-cigarettes as >5 on a 0-10 scale, c) willing to use an e-cigarette as part of the trial, d) have a smartphone that can receive text messages and has access to the internet or have an e-mail account they check daily (necessary for daily diary completion) and e) be at least 21 years of age. Exclusion criteria include a) purchasing an e-cigarette within the last six months, b) weekly use of e-cigarettes over the last six months, c) any e-cigarette use in the past 30 days, d) use of tobacco products other than cigarettes on ten or more days in the past 30 days, e) current use of cessation medications, f) pregnant, trying to become pregnant, or breastfeeding, g) recent history of cardiovascular distress in the last three months, h) history of a seizure disorder, or i) household member currently enrolled. We will stratify group assignment based on age (21-30 vs. 31+) and motivation to quit (0-6 vs 7-10) to prevent these variables from being confounded with group.

**C3. E-cigarettes and e-liquids:** The best exemplars will be chosen from each of two device type categories based on market share data. Currently these include the Mirage DNA 75C e-cigarette (customizable tank style), and a JUUL e-cigarette and pre-filled pods (pod).

Participants will be provided with one device, one charger, and a choice of e-liquid flavors. Participants will be able to choose up to two flavors (to allow for switching of flavors during sampling) from a menu of four flavors. For the customizable tank/Mirage device, e-liquid is sold separately which is the case with all customizable tanks. E-liquid will be available in a wide array of flavors, and will be provided in 12 mg/ml nicotine concentration. For the pod/JUUL devices, we will provide each participant with one pre-filled e-liquid pod for each day of sampling. These pods provide enough nicotine to compare to one pack of cigarettes, and thus one pod per day should be sufficient. E-liquid will be 5% nicotine, which JUUL states is the most popular nicotine concentration they sell. All participants will receive instructions on how to operate their device, fill it with e-liquid or replace the pods, and be given a lab phone number to call with questions. Participants assigned to the customizable tank device will be shown how to adjust their customization settings.

**C4. Compensation** Participants will receive \$50 for the screening/randomization if they are eligible and \$15 if they are not. Participants will receive \$50 for the Week 3 visit, \$20 each for the Week 1 and Week 2 phone calls, and a \$50 completion bonus if they complete all assessments. Participants will also receive up to \$25/week for completing daily diaries (up to \$75). Thus, participants who attend all visits and complete all diary entries could earn \$265.

## C5. Measures

**C5a. Screening Assessments:** Preliminary eligibility will be determined on the phone before participants are either consented electronically or invited for an in-person visit to provide consent. Alternatively, participants may complete a Redcap survey to determine initial eligibility. Participants will see a script that briefly explains the study. Consented participants will attend an in-person visit where they complete screening questionnaires related to demographics, tobacco use history, and expired carbon monoxide.

**C5a. Measures of Subjective Effects:** Subjective effects will be assessed using a modified version of the Cigarette Evaluation Questionnaire (mCEQ), which assesses product satisfaction, psychological reward, craving reduction, enjoyment of sensations in the respiratory tract, and aversion. First, participants will sample their usual brand cigarette to standardize time since last cigarette. Participants will then sample their assigned e-cigarette and e-liquid. Immediately after sampling, participants will complete the mCEQ.

**C5b. Measures of Relative Reinforcement:** Relative reinforcement will be assessed using a lab-based choice task, a well-validated measure of reinforcement value. After participants sample their assigned product, they will complete choice task in which over a period of 30-minutes and 10 trials, participants choose between taking two puffs of the e-cigarette, two puffs of their usual (own) brand cigarette, or abstaining from both. Participants in the control group will choose between their usual brand cigarette and abstaining. In this case, the task will measure the impact of device type on changes in the relative reinforcement value of smoking compared to using the e-cigarette. The primary outcome is the number of choices to smoke. A secondary measure of reinforcement value will be purchase tasks—hypothetical tasks in which participants estimate the intensity with which they would use cigarettes and e-cigarettes at a variety of prices. The purchase tasks can be used to calculate several demand parameters, which are estimates of reinforcement value. Additional dependence measures will be included. [name] is utilizing these measures in recently completed and upcoming projects.

**C5c. Measures of Tobacco Use and Biomarkers:** Daily cigarette use will be captured using an electronic daily diary (<2 min/day) in which participants report the number of e-cigarette puffing episodes per day and the number of cigarettes they smoked. This electronic daily diary was used in [name] recently completed trial with compliance > 90%. We will collect expired breath carbon monoxide at Randomization and the Week 3 visit, which provides an objective measure of recent smoke exposure but is unaffected by e-cigarette aerosol.

[figure not shown]
**C5d. Other Self-Report Questionnaires:** We will also use questionnaires to assess demographics, tobacco use history, expectancies, perceived health risks, and adverse events over time.

## C6. Statistical Analysis, Power, and Predicted Outcomes

**C6a. Statistical Analysis:** We focus on changes in reinforcement value of cigarettes because the public health impact of e-cigarettes will be driven by changes in the use of cigarettes, rather than any direct effects of e-cigarettes. Our primary outcome is the percentage of choices for each participant to smoke the conventional cigarette during the choice task at Week 3 (ranging from 0 to 100%). A one-way ANOVA model will be used to compare the e-cigarette groups, while excluding the control group, to examine the effect of e-cigarette type. If there is no significant difference between e-cigarette types, e-cigarette participants will be combined and compared to the control group via a t-test to examine the effect of e-cigarette sampling. Other outcomes will be analyzed using general linear mixed models (GLMMs) controlling for baseline values and repeated measurements per participant will be used to examine group, time, and group by time interactions. Our secondary aim focuses on the average number of cigarettes smoked per day during Week 3 while also examining average e-cigarette puffing episodes, expired carbon monoxide. These outcomes will be examined in a similar manner via GLMMs. We will also conduct exploratory analyses to determine whether the effect of e-cigarette type or e-cigarette sampling depended on individual characteristics such as age, gender, race, and motivation to quit. Given the innovative and exploratory nature of this trial, there are no existing datasets that directly apply for the purposes of conducting a power calculation. However, a sample size of 30 per e-cigarette group will provide 80% power to detect moderate between-group differences in a one-way ANOVA comparing the primary outcome with a two-sided alpha=0.05.

**C7c. Predicted Outcomes:** We hypothesize that the pod e-cigarette will result in further reductions in choices to smoke during the choice task and in cigarette smoking (Figure 2).

**C8. Future Directions:** The goal of the proposed application is to gain preliminary data on the impact of e-cigarette type. An R01 grant application will follow the proposed project and will include a longer sampling period, longer follow up period, a more thorough investigation of the health effects of e-cigarette types, and a full investigation of any critical moderators (e.g., age).

**C9. Timeline:** The proposed study will take one year. The first three months will be devoted to study start up, measurement finalization, IRB approval, obtaining product, etc. Our prior studies will steer this process efficiently. We will recruit approximately eight participants/month for 9 months, until 100 participants have been randomized. An R01 grant application will be submitted in the Fall of 2020.

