#### 1.2 Study Procedures, Materials, and Potential Risks:

##### Study Procedures:

Participants will be screened over the phone to determine initial eligibility. Alternatively, participants may complete a redcap survey to determine initial eligibility. Participants will see a script that briefly explains the study. Once participants have been determined to be initially eligible, they will be invited to participate in the consent process. The consent process will take place via one of the following modalities: 1) Remote electronic consent (e-consent) via REDCap facilitated with a discussion over the phone, 2) Remote consent via doxy.me, or 3) in-person consent (in-person visit at start of Visit 1). We have built in the option for electronic consent to reduce the length of the first in-person visit and while still providing ample time for the consent process. Consented participants will be asked to attend an in-person screening session. We will provide transportation via a taxi cab company (Yellow Cab) for participants who are eligible, but do not have reliable transportation to in-person visits. We will pay the cab company directly, the participant will not need to contribute. Participants will be asked to provide a carbon monoxide sample to confirm smoking status, and women will provide a urine sample for pregnancy testing. Participants will then complete a series of interview-administered and participant-administered questionnaires that assess brief medical history, tobacco use history including prior and current e-cigarette and cigarette use, current use of smoking cessation products, and demographics. After all questionnaires have been completed, study staff will determine participant eligibility.

Participants who are eligible will then complete additional baseline questionnaires including measures of nicotine dependence. Participants will be randomized as described above and will have the opportunity to sample their usual brand cigarette and their assigned e-cigarette and e-liquid for the first time. After sampling each product, participants will complete additional questionnaires and complete the preference assessment where they choose between their cigarette and assigned e-cigarette. At the end of Visit 1, participants will receive a three-week supply of e-liquid to take home with their assigned e-cigarette, will be enrolled in the daily electronic diary system, and will be provided with instructions for completing diaries.

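### Randomisation is stratified by age and motivation to quit, but the primary ANOVA and the follow-on t-test ignore the strata; if these predict choices to smoke, both tests are conservative and less powerful than an adjusted analysis.

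*Combined protocol and SAP*

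**What the plan says.** Section C2 (Participants) sets the allocation: "We will stratify group assignment based on age (21-30 vs. 31+) and motivation to quit (0-6 vs 7-10"). The reason given is to keep the two variables from being confounded with group. Allocation is 1:2:2, with 20 controls and 40 in each e-cigarette arm.

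Section C6a defines the endpoint: "Our primary outcome is the percentage of choices for each participant to smoke the conventional cigarette during the choice task at Week 3". The primary test is "A one-way ANOVA model will be used to compare the e-cigarette groups, while excluding the control group". If it is not significant, "e-cigarette participants will be combined and compared to the control group via a t-test to examine the effect of e-cigarette sampling". No covariate or stratum is named for either test.

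Adjustment appears in C6a only for the remaining endpoints: "Other outcomes will be analyzed using general linear mixed models (GLMMs) controlling for baseline values". Even there the strata are not named. Age and motivation to quit come back once, in exploratory analyses of whether the effect "depended on individual characteristics such as age, gender, race, and motivation to quit". Nothing elsewhere in the document puts the stratification factors into either test of the primary outcome.

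**The concern.** Stratified allocation forces the arms to be nearly alike in age group and motivation. The difference between arm means then carries almost no variation from those factors. A test that leaves them out still estimates its error from total variance, including the part that the design has removed from the comparison. If the strata predict the outcome, the standard error is too large for the design, the confidence interval is too wide, and the true type I error is below 5%.

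At stake is precision in a small trial meant to inform a larger grant application. The follow-on comparison is exposed in the same way and has only 20 controls.

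**Working it through.** **Inputs from the documents.** Two binary stratification factors; 20/40/40 randomised; two-sided alpha 0.05; 30 per e-cigarette group as the basis of the power statement; an outcome built from 10 choice trials (C5b).

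**Assumed, because the documents do not give them.** The share of outcome variance explained by the strata (R², taken as 0 to 30%); a standardised difference d = 0.5; a normal outcome with equal variances; permuted blocks of 5 or 10 within strata; stratum splits of 75/25 for age and 50/50 for motivation; R² divided equally between the factors.

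**The plan's own figure.** C6a claims 80% power at 30 per group for a moderate difference, without a number. By noncentral t, 80% at 30 per group requires d = 0.736; at d = 0.5 the power is 47.8%. With 40 per group the values are d = 0.634 for 80%, and 59.8% at d = 0.5. The stated 80% can be neither confirmed nor refuted without a numerical effect, so R² effects are shown at d = 0.5 and again near 80% power.

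**Formulas.**
- Excess in the unadjusted standard error: 1/√(1−R²) − 1.
- Large-sample true type I error of the unadjusted test: 2·[1 − Φ(1.96/√(1−R²))].
- Power of the adjusted test: noncentral t at effect 0.5/√(1−R²), with two further degrees of freedom spent.

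Example at R² = 10%: 1/√0.90 = 1.054, so the standard error is 5.4% too large; 1.96 × 1.054 = 2.066, giving a type I error of 0.039.

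| R² | SE excess | Type I error, large-sample | Adjusted power, 40 v 40 | Adjusted power, 30 v 30 | Adjusted power, 80 v 20 |
|---|---|---|---|---|---|
| 0 | 0% | 0.050 | 0.598 | 0.477 | 0.508 |
| 5% | 2.6% | 0.044 | 0.620 | 0.497 | 0.529 |
| 10% | 5.4% | 0.039 | 0.643 | 0.518 | 0.551 |
| 20% | 11.8% | 0.028 | 0.694 | 0.567 | 0.600 |
| 30% | 19.5% | 0.019 | 0.751 | 0.624 | 0.658 |

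The unadjusted starting points at R² = 0 are 0.598, 0.478 and 0.508.

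**Simulated type I error** (20,000 runs, blocks of 5; R² = 0/5/10/20/30%).
- Device comparison, unadjusted, no loss: 0.051/0.048/0.039/0.029/0.021.
- Device comparison, unadjusted, 25% random loss: 0.050/0.046/0.041/0.037/0.030. Loss partly undoes the balance, so the conservatism shrinks.
- Device comparison, adjusted: 0.046 to 0.053 throughout.
- Pooled e-cigarette v control, unadjusted, no loss: 0.052/0.045/0.038/0.030/0.021; adjusted, 0.048 to 0.052.
- Pooled comparison counted only when the ANOVA was non-significant, as planned (8,000 runs, R² = 20%): 0.031 unadjusted, 0.052 adjusted.

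**Is stratification the cause?** With simple randomisation at R² = 30%, the unadjusted type I error is 0.052 for the ANOVA and 0.049 for the t-test. With stratified allocation both are about 0.02.

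**Does the bounded outcome matter?** With the outcome rounded and clipped to 0-10, unadjusted type I error for the device comparison was 0.053/0.046/0.039/0.032/0.024 and adjusted 0.048 to 0.053. Power, unadjusted v adjusted, was 0.558 v 0.590 at a latent R² of 10% and 0.556 v 0.638 at 20%.

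**How strong must the strata be?** For a binary factor with prevalence p explaining half of R², the difference in means is √[(R²/2)/(p(1−p))] SD. At R² = 5% this is √(0.025/0.25) = 0.32 SD for motivation and √(0.025/0.1875) = 0.37 SD for age. At 30% it is 0.77 and 0.89 SD, which is best read as an upper bound.

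**The case against.** The strongest reply is that nothing here is invalid. C2 says why the trial stratifies, which is to avoid confounding, and balance achieves that without adjustment. The estimate is unbiased and the error is on the safe side. **This stands**: the point concerns efficiency, not validity.

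The size rests on an unknown R². At 5% the gain is about 2 points of power, and at zero there is none. **This stands too**, and it is why the conclusion is conditional and the lower rows deserve most weight.

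The choice of d = 0.5 also shows the gap near its widest. At 40 per arm and d = 0.634, where unadjusted power is about 80%, simulated power unadjusted v adjusted is 0.814 v 0.827, 0.809 v 0.837, 0.825 v 0.878 and 0.837 v 0.920 at R² of 5/10/20/30%. Those gaps are about 1, 3, 5 and 8 points. Nor does unadjusted power fall below its no-stratum-effect level: at d = 0.5 and 40 per arm it is 0.595/0.595/0.603/0.608/0.613 across R² of 0 to 30%. The loss is therefore relative to the adjusted test, and taking 60% as a fixed starting point overstates it by about a point at R² = 30%.

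Finally, the allocation method and stratum sizes are not described, and controls choose between two options rather than three, so their variance may differ. The 80 v 20 figures are the least secure for that reason. None of this removes the mismatch between design and analysis, and the preliminary label is no reason to leave precision unused.

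**Conclusion.** The concern holds. The plan randomises within strata and analyses the primary outcome as if it had not. If the strata predict choices to smoke, both tests are conservative and have less power than a test adjusted for the strata; if they do not, both keep their 5% level.

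For R² of 5-10% the power gain from adjustment is about 1-3 points near 80% power, and about 2-5 points at d = 0.5. At 20% it is about 5 to 10 points. These sizes depend on the assumed R², effect size, normal outcome and blocked allocation. The direction of the effect and the absence of type I error inflation do not depend on the particular R² chosen. The change is worth making because its cost is close to nil, but the trial would not be unsound without it.

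**What to change.** In C6a, replace the one-way ANOVA with a prespecified linear model (ANCOVA) of Week 3 percentage of choices to smoke on device, age stratum and motivation stratum, using the strata as recorded at randomisation. Put the same two terms in the pooled e-cigarette v control comparison. Keep the unadjusted ANOVA and t-test as sensitivity analyses.

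Any further covariate is optional and should be a single named measure taken before randomisation, such as baseline cigarettes per day. The Visit 1 choice task should not be used. Under Study Procedures (section 1.2) it comes after assignment and first use of the product: "Participants will be randomized as described above and will have the opportunity to sample their usual brand cigarette and their assigned e-cigarette". It may therefore already carry a device effect.

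The cost is two or three lines of text, with no new data. The two terms use 2 of 78 error degrees of freedom at 40 per arm, or 2 of 58 at 30 per arm. If the strata explain nothing, the loss is about 0.5 point of power or less (for example, 0.594 to 0.591 with no loss to follow-up, and 0.475 to 0.472 with 25% loss). Two more uninformative covariates would bring it to about 1 point, or 2 points with 25% loss, which is a reason to keep the model short.
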